# **6.1.5 Treatment Emergent Period**

The treatment emergent period is defined as the period of time from the date of the first dose of any study drug through either 30 days after the date of the last dose (latest of any study drug) or the first date of subsequent anticancer therapy, whichever is earlier.

# 6.2 Imputation Rules for Missing and Partial Data

In general, other than for partial dates, missing data will not be imputed and will be treated as missing. The algorithms for imputation of partial dates vary depending upon the parameter.

# **6.2.1 Adverse Events, Concomitant Medications, Prior/Subsequent Anticancer Therapies, Initial Diagnosis**

Imputation of partial dates will be made for AE onset and stop dates, start and end dates of concomitant medication, start date of prior/subsequent anticancer therapy, and date of initial diagnosis. If dates are completely missing, no imputation will be made. For any partial date with missing year, no imputation will be made.

The general rule for imputation is:

- If only day is missing, then the 15th of the month will be used.
- If only year is present, then June 30th will be used.

If such imputed date for initial diagnosis or prior anticancer therapy is on or after date of first dose date of any study drug, then date of first dose – 1 will be used. If such imputed date for subsequent anticancer therapy is before date of last dose (latest of any study drug), then date of last dose + 1 will be used.

If the imputed date is for an AE start date and is in the same year and month as but before the first dose date of any study drug, then the first dose date will be used, or if the imputed AE start date is after the AE end date, then the AE end date will be used. If the imputed date is for an AE start date and is in the same year and month as but after the last dose date (latest of any study drug) + 30 days, then the last dose date + 30 days will be used.

If the imputed date is for an AE end date and is after the death date, then the death date will be used, or if the imputed AE end date is before the AE start date, then the AE start date will be used.

ACE-LY-003 Parts 2-3 Statistical Analysis Plan Version 1.0: 31Mar2022

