5.4 MISSING DATA HANDLING

General Considerations: Subjects lost to follow-up (or who dropped out) will be included in statistical analyses up to the point of their last evaluation.

Duration of Response and Progression-Free Survival: Data for subjects without disease progression or death will be censored at the date of the last tumor assessment and before the initiation of alternative anticancer therapy. The details of the censoring rules will be provided in the Statistical Analysis Plan (SAP).

Time-to-Next Treatment: Data from subjects who have not received subsequent therapy will be censored at the earliest of death or the last time that lack of administration of a new therapy was objectively documented. The details of the censoring rules will be provided in the SAP.

Safety: Missing or partial start and end dates for AEs and concomitant medications will be imputed according to prespecified, conservative imputation rules. The details will be provided in the SAP. No other imputation of values for missing data will be performed.

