#### 6.1.3 Definition of Prior and Concomitant Medication

For the purpose of inclusion in prior and/or concomitant medication summaries, incomplete medication start and stop dates will be imputed as detailed in Section 6.2. Based on imputed start and stop dates:

- Prior medications are defined as medications with a start date occurring before the date of first dose of any study drug.
- Concomitant medications are defined as medications that:
  - Had start date on or after the first dose date of study drug and either within 30 days after the last dose date (latest of any study drug), or before the first dose date of subsequent anticancer therapy, whichever is earlier, or
  - Had start date before first dose date of any study drug and were either ongoing or had a stop date on or after first dose date.
- Medications that meet the criteria for both prior and concomitant medication will be classified as both prior and concomitant medication.
- Medications with completely missing start and stop dates will be considered as both prior and concomitant medications.

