#### 7.6.5 Time-to-Next Treatment

# 7.7 Analyses of Safety Endpoints

Safety analyses will be performed by treatment arm on the all-treated population.

Analyses of AEs will be performed on treatment-emergent AE (TEAE) data, unless otherwise specified. TEAEs are defined as those adverse events with onset or worsen date during the treatment emergent period, which is defined in Section 6.1.6. All AE terms will be coded by

MedDRA, and severity will be graded per CTCAE version 5.0.

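### SAP 6.2.1 assigns no date to an adverse event whose start date is wholly missing or lacks the year, contrary to Protocol 5.4, so on a literal reading such an event is left out of the treatment-emergent tables

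*SAP*

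**What the plan says.** **Protocol 5.4 (Missing Data Handling, Safety)** states: "Missing or partial start and end dates for AEs and concomitant medications will be imputed according to prespecified, conservative imputation rules". It leaves the details to the SAP.

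**SAP 6.2** sets the general rule: "In general, other than for partial dates, missing data will not be imputed and will be treated as missing". **SAP 6.2.1** applies it to AE onset and stop dates, among others. A date lacking only the day becomes the 15th, and a date with only the year becomes 30 June. Two further cases get nothing: "If dates are completely missing, no imputation will be made" and "For any partial date with missing year, no imputation will be made".

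**SAP 6.1.5** gives the window: "The treatment emergent period is defined as the period of time from the date of the first dose of any study drug". It closes 30 days after the last dose or at the first subsequent anticancer therapy, whichever is earlier. **SAP 7.7** states: "TEAEs are defined as those adverse events with onset or worsen date during the treatment emergent period". It also states: "Analyses of AEs will be performed on treatment-emergent AE (TEAE) data", unless otherwise specified.

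For medications, **SAP 6.1.3** has a default: "Medications with completely missing start and stop dates will be considered as both prior and concomitant medications". No comparable default is given for AEs. **SAP Section 8** lists two changes from the protocol: the efficacy-evaluable definition and the start date for the time-to-event endpoints.

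**The concern.** The protocol names two kinds of incomplete AE date, missing and partial, and promises conservative handling of both. The SAP imputes only partial dates that carry a year. The remaining AEs then meet a definition that needs a date they do not have.

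Safety is the primary objective of Part 3 and a secondary objective of Part 2, and the groups are small. Leaving an event out of a table cannot raise its incidence, so any error from this rule goes one way, towards a more favourable safety profile. That is the direction a conservative rule is meant to prevent.

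**Working it through.** The plan states no figure on this point, so there is nothing to reproduce. The check is a trace of the rules followed by a scale calculation.

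**Rule trace for an AE whose start date is wholly missing or lacks the year**

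1. SAP 6.2.1: no date is assigned.
2. SAP 6.1.5: the window is bounded by calendar dates, so the onset cannot be placed inside it.
3. SAP 7.7: the TEAE definition is met only if a worsening date inside the window is recorded.
4. SAP 7.7 and 7.7.1: AE tables use TEAEs unless otherwise specified. The one row expressly widened beyond them is for COVID-19 AEs. The row for serious events is not labelled treatment-emergent but comes under the general statement in 7.7. The special- and clinical-interest tables in 7.7.2 come under it too.
5. Result: without such a worsening date, the AE is not counted in the TEAE-based tables.

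**Comparison with AEs that have better dates.** SAP 6.2.1 also adjusts AE starts after imputation. A start imputed before the first dose but in the same month and year is moved to the first dose date. A start imputed later than 30 days after the last dose, but in the same month and year as that day, is moved back to it. Both steps favour counting the AE. The gap is therefore confined to AEs with no usable year.

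**Comparison with the protocol.** Protocol 5.4 covers missing dates; SAP 6.2.1 excludes them from imputation; SAP Section 8 is silent.

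**Scale.** Suppose one subject has an undated AE and no other occurrence in the same table row. The loss in incidence is 100 × 1/n percentage points:

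| Group | n | Loss (points) |
|---|---|---|
| Part 2, Cohort 1 (SAP 3.2, upper limit) | 40 | 1/40 = 2.5 |
| Part 3, upper end (SAP 3.2) | 32 | 1/32 = 3.1 |
| Part 3, lower end (SAP 3.2) | 26 | 1/26 = 3.8 |
| Selected dose, 6 + about 14 (SAP 3.1) | 20 | 1/20 = 5.0 |
| Dose group that stays at 6 (SAP 3.1) | 6 | 1/6 = 16.7 |

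If the subject also has a dated occurrence in that row, the loss is zero. The documents give no count of undated AEs, so these figures show the effect of one affected subject and do not estimate the effect in the trial.

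**The case against.** **Exclusion is inferred.** A reader might take the SAP to say that undated AEs are dropped. It does not. It withholds a date and defines a TEAE by date; exclusion follows only if those rules are programmed literally. An AE with a recorded worsening date in the window still qualifies. This limits the claim but leaves the difference from Protocol 5.4 in place.

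**The details were delegated.** Protocol 5.4 leaves the rules to the SAP, and SAP 6.2.1 does contain protective AE rules. It is arguable whether a delegated detail belongs in Section 8. But the protocol sentence names missing dates, and delegating the choice of rule does not remove them from its scope.

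**The medication contrast is loose.** A reader might infer that the SAP chose to be less careful with AEs than with medications. The documents do not show that. The medication default applies only when both start and stop dates are wholly missing; it classifies and does not impute. The no-imputation sentences in 6.2.1 cover concomitant medications as well. The contrast shows a default that was not written for AEs, and no more.

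**The case is rare and partly covered.** Protocol 6.3.2 requires start and end dates for each AE, Protocol 7.4 requires complete case report forms, and serious events are reported within 24 hours. Data listings are planned (SAP 6), deaths have their own tables and listing (SAP 7.7.1), and SAP Appendix 2 calls for narratives of deaths, other serious events and discontinuations, although its window for qualifying events is also date-based. This stands and keeps the point modest.

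**Dose finding.** A reader might infer that escalation in Part 3 is at risk. It is not: those decisions use rolling review of dose-limiting toxicities at the end of Cycle 1, not the TEAE tables.

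**Document versions.** The SAP was written to Protocol Amendment 6 and the supplied protocol is later. The change summary at the front of the supplied protocol does not list Section 5.4 as altered in that amendment. The comparison here rests on the texts as supplied.

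**Conclusion.** The point holds as a narrow conflict between the two documents. The protocol promises conservative imputation of missing AE dates, the SAP imputes nothing when the date is wholly missing or lacks the year, and the departure is not recorded. On a literal reading, AEs of this kind without a worsening date in the window are left out of the TEAE tables, so incidence can be understated by this rule but not overstated.

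The size is probably small and its frequency is unknown. For one affected subject the loss is between 2.5 and 5 points in the groups that matter most for reporting. The 16.7-point figure is the extreme case, a dose group that ends with 6 subjects, and should not be read as the expected effect. All the figures assume that the subject has no other occurrence in the same row. The change is worth making because it costs almost nothing and brings the SAP into line with the protocol.

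**What to change.** Add to SAP 6.2.1, with a matching sentence in 7.7: an AE whose start date is completely missing, or lacks the year, is counted as treatment-emergent unless its end date or other recorded information shows either that it started before the first dose without later worsening, or that it started after the treatment-emergent period. Flag these AEs in a listing so that readers can see how many there are.

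The exceptions are needed because Protocol 6.3.1 has AEs collected from consent and allows some reports after the 30-day period. An end date before first dose would not by itself screen out an event that began before dosing and continued, or one that began late.

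If the sponsor prefers the present rule, Section 8 should state it as a departure from Protocol 5.4 and give the reason. In the same edit, the cross-reference in 7.7 to Section 6.1.6 should point to 6.1.5, where the treatment-emergent period is defined.

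The cost is a short addition to the SAP and one programming condition. The downside is that a few pre-dose or late events may be counted, making some incidences slightly less favourable.

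### SAP 6.2.1 dates a year-only AE before treatment when its recorded year is the first-dose year and first dose falls from 1 July to 31 December, so an on-treatment AE can leave the TEAE tables

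*SAP*

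**What the plan says.** SAP 6.2.1 imputes partial AE onset dates. A missing day becomes the 15th of the month. For a year alone, "If only year is present, then June 30th will be used". Three adjustments to the start date follow:

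- It is moved to first dose if it "is in the same year and month as but before the first dose date of any study drug".
- It is capped at the end of the event: "or if the imputed AE start date is after the AE end date, then the AE end date will be used".
- It is moved back to last dose plus 30 days if it "is in the same year and month as but after the last dose date (latest of any study drug) + 30 days".

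Onsets with no date or no year are left alone: "If dates are completely missing, no imputation will be made", and "For any partial date with missing year, no imputation will be made".

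SAP 6.1.5 runs the treatment-emergent period from first dose to 30 days after last dose "or the first date of subsequent anticancer therapy, whichever is earlier". SAP 7.7 counts an AE as a TEAE if its onset or worsening date lies in that period, and bases the AE analyses on TEAEs unless stated otherwise. (It cites Section 6.1.6 for the period; the definition is in 6.1.5.) Protocol 5.4 commits to conservative, prespecified imputation of missing or partial AE dates and leaves the details to the SAP. SAP 8, on changes from the protocol, has no entry on this.

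**The concern.** The first-dose adjustment is there to keep an event with an uncertain onset inside the treatment-emergent period. It does so for an onset whose day is missing in the month of first dose. For a year-only onset it requires a month match, although the month is exactly what is unknown. Whether the event is counted then depends on the calendar date of first dose and not on anything recorded about the event.

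Elsewhere in SAP 6.2.1 no month match is needed. An imputed diagnosis or prior-therapy date on or after first dose is reset to the day before it, and an imputed subsequent-therapy date before last dose is reset to the day after it. Only the AE start-date rules carry the extra condition.

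Safety is the primary objective of Part 3, with about 26 to 32 subjects. An AE that leaves the TEAE tables only because its month is unknown understates toxicity there. One subject is 1/32 = 3.1% to 1/26 = 3.8% of a table row.

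**Working it through.** The plan gives no figure on this point to reproduce. The inputs are the rules in SAP 6.2.1, 6.1.5 and 7.7, and the projected dates in Protocol 3.2. All counts below are of calendar dates in a 365-day year, not of AEs.

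**1. Can the first-dose adjustment act on a year-only onset?** It needs a first dose in June and 30 June earlier than first dose. The latest June first dose is 30 June itself, so the second condition fails. For any other month the first fails. It acts on 0 of 365 first-dose dates.

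**2. Can another adjustment rescue the event?** The end-date cap and the last-dose cap only move an onset earlier, so neither can bring a pre-dose onset into the period. A known end date on treatment does not help.

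**3. Which first-dose dates are affected, when the AE's recorded year is the first-dose year?**

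- July to December: 31 + 31 + 30 + 31 + 30 + 31 = 184 dates, onset before first dose (184/365 = 50.4%).
- January to June: 31 + 28 + 31 + 30 + 31 + 30 = 181 dates, onset on or after first dose.

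If the recorded year is the year after first dose, 30 June always follows first dose and no date is affected.

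**4. Example.** First dose 1 October 2020; AE start recorded as 2020; AE end 20 November 2020. The imputed onset is 30 June 2020. Study day = 30 June − 1 October = −(31 + 31 + 30 + 1) = −93. Duration = 93 + 50 + 1 = 144 days. The AE is not a TEAE unless it has a worsening date in the period. With onset at first dose it would be study day 1, with a duration of 50 + 1 = 51 days.

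**5. The closing end.** The last-dose cap also needs a month match, so it can act on 30 June only if last dose plus 30 days falls in June. If the period closes from 1 January to 31 May (31 + 28 + 31 + 30 + 31 = 151 dates), a year-only AE from that year is dated after it. Example: last dose 1 March 2021, period end 31 March 2021, AE recorded as 2021, imputed onset 30 June 2021. Here a known end date inside the period does rescue the event, because the end-date cap pulls the onset back to it. A worsening date inside the period also keeps it. The cap refers to last dose plus 30 days, so it does not follow the period end when subsequent therapy closes the period earlier.

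**6. Does the affected first-dose range occur?** Protocol 3.2 puts the Part 2 cut-off at about 25 August 2023, about 23 months after the last subject's first dose. 25 August 2023 − 23 months = 25 September 2021, which is 31 + 31 + 25 = 87 days after 30 June 2021. Both figures are approximate, but this estimate would have to be at least 87 days too late to leave the range. First-dose dates for other subjects, and for all of Part 3, are not given.

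**The case against.** The strongest objection is that the trigger is rare where the rule fails. On the first-dose side the event must begin between first dose and 31 December of that year, at most 184 days. Those are the most closely watched months: weekly visits in Cycle 1, every two weeks in Cycle 2, then monthly through Cycle 13 (Protocol 3.1). AEs are assessed at every evaluation and recorded with start and end dates (Protocol 6.3.2). An onset whose month is unknown should be uncommon. This stands, and it is why the point is minor.

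Other outputs also limit the harm. Data are listed by subject (SAP 6). Deaths have their own tables and listing (SAP 7.7.1). Narratives cover deaths, SAEs, AEs of special interest and AEs leading to discontinuation (SAP Appendix 2). A misdated AE therefore need not vanish from the report. This stands too, but it does not correct the TEAE counts.

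Protocol 5.4 does not define conservative. Reading it as counting a doubtful event as treatment-emergent is an interpretation, though the usual one for safety. Some genuine pre-dose events are possible, since Protocol 6.3.1 collects AEs from consent. However, Protocol 4.1.3 requires recording from first dose, and the Part 2 and Part 3 schedules show no AE collection at screening, so an on-treatment onset is the more natural default.

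Three stronger readings are tempting, and the documents do not support them:

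- That every year-only AE is lost in a subject first dosed after 30 June. AEs recorded in a later year are not dated before treatment.
- That 184 of 365 means half of year-only AEs are lost. It is a share of calendar dates; the distribution of first doses and the number of year-only AEs are not given.
- That AEs with no onset year are shown to be lost. The SAP gives no default for them, whereas for drugs "Medications with completely missing start and stop dates will be considered as both prior and concomitant medications". That is a missing default, not a shown error.

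**Conclusion.** The concern holds in this limited form. For a year-only AE recorded in the first-dose year, SAP 6.2.1 gives a pre-treatment onset for every first dose from 1 July to 31 December. The adjustment meant to prevent this cannot act, and no other rule in the documents restores the event, apart from a worsening date in the period. The closing-end failure is narrower, because a known end date inside the period also rescues the event. Neither result is conservative in the sense that Protocol 5.4 needs.

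The mechanism follows directly from the text. Its effect on the tables cannot be sized without the number of year-only AEs. Given the visit schedule it is probably small, and DLT decisions do not depend on this rule. Severity: minor.

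**What to change.** In SAP 6.2.1, for AE onsets with only the year recorded, add:

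1. If the recorded year is the first-dose year and 30 June is before first dose, use the first dose date. Exception: the recorded parts of the AE end date (full date, month and year, or year) place the end before first dose. An end date imputed from year alone in the first-dose year must not trigger the exception, since it too would become 30 June.
2. If the recorded year is the year in which the treatment-emergent period (SAP 6.1.5) ends and 30 June is after that end, use the period end date. Keep the cap at the AE end date when that date is known.

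Apply the existing end-date cap before rule 1, so that an imputed end date cannot pull the onset back before first dose. The exception covers partial end dates: with first dose 1 October 2020, start 2020 and end August 2020, the event stays outside the TEAE tables. With these rules the on-treatment events in the working are kept at both ends.

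A default for AEs with no onset year could be added for consistency with SAP 6.1.3. It is optional.

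The cost is a few lines of SAP text and the matching date derivation, with no reference to results. The downside is that a few AEs that truly began before dosing or after the period may be counted as TEAEs. The current rule already accepts this for year-only AEs when first dose is on or before 30 June.

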#### 7.6.1 Overall Response Rate

Best overall response is defined as the best disease outcome over all response assessments on or before the initiation of subsequent anticancer therapy. Best overall response categories include CR, PR, SD, and PD. The number and percentage of subjects in each best overall assessment category will be presented by treatment arm. ORR will be defined as the proportion of subjects who achieve a CR or PR according to the Lugano Classification for NHL (Cheson et al. 2014), as assessed by investigators. ORR will be calculated, and the corresponding 2-sided 95% confidence interval will be derived.

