#### 7.6.2 Duration of Response

The DOR is defined as the interval from the first documentation of CR or PR to the earlier of the first documentation of definitive disease progression or death from any cause. Following first documentation of CR or PR, subjects who do not experience a disease progression or death will be censored using the same rule for PFS as described in Table 1. DOR is calculated as date of disease progression or death (censoring date for censored subjects) – date of achieving the first CR, CRi, PR, or nPR + 1. Kaplan-Meier (KM) methods similar to those described in Section 7.6.3 will be used to estimate event-free curves and corresponding quantiles (including the median) by

arm.

If at least 1 responder has an event of death (and without progression prior to death) due to Coronavirus disease 2019 (COVID-19), a sensitivity analysis will be conducted to assess for the potential impact of deaths due to COVID-19. Subjects with death related to COVID-19 infection (and without progression prior to death) will be censored at their last evaluable assessment prior to their COVID-19 related death date.

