**Table 1. PFS Censoring** 

Situation Date of Event or Censoring Outcome			
Situation 1: PFS events include death or first disease progression as assessed by			
investigator that occurred at or prior to the earliest of data analysis cutoff date,			
alternative cancer therapy start date, and discontinuation from study (and not			
immediately following ≥2 consecutively missed visits where CT scan was required).			
Date of event is defined as follows:			
Death before first disease assessment	Date of death	Event	
INV-PD or death before study exit or	Earlier date of INV-PD or death	Event	
data cutoff			
Situation 2: All other cases not meeting	ng 'Situation 1' will be censored as	follows:	
No baseline assessment	First dose date of any study	Censored	
No baseline assessment	drug	Censored	
No adequate* post-baseline	First dose date of any study	Censored	
assessment		Censored	
	drug		
No INV-PD or death at the time of data	Date of last adequate* INV	Censored	
cutoff	assessment before data cutoff		
No INV-PD or death before lost to	Date of last adequate* INV	Censored	
follow-up or study exit	assessment before lost to		
	follow-up or study exit		

No INV-PD or death before start of	Date of last adequate* INV	Censored
subsequent anticancer therapy	assessment before start of	
	subsequent anticancer therapy	
INV-PD or death immediately after two	Date of last adequate* INV	Censored
INV-PD or death immediately after two or more consecutively missed visits	Date of last adequate* INV assessment before missing two	Censored

Abbreviation: INV=investigator

PFS will be calculated as date of disease progression or death (censoring date for censored subjects) – date of first dose of any study drug + 1.

Kaplan-Meier methods will be used to estimate the event-free curves by arm and corresponding quantiles (including the median). The proportion of subjects who are progression-free and the corresponding 95% CI will be estimated based on KM method at select timepoints by treatment arm.

If at least 1 subject has an event of death (and without progression prior to death) due to COVID-19, a sensitivity analysis will be conducted to assess for the potential impact of deaths due to COVID-19. Subjects with death related to COVID-19 infection (and without progression prior to death) will be censored at their last evaluable assessment prior to their COVID-19 related death date.

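### The rule for partial subsequent-therapy dates is never checked against documented progression, so it can turn a PFS or DOR event into a censoring and can move the end of the treatment-emergent window

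*SAP*

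**What the plan says.** SAP 6.2.1 gives one rule for partial start dates of subsequent anticancer therapy. "If only day is missing, then the 15th of the month will be used" and "If only year is present, then June 30th will be used". The single correction specific to these dates is the last-dose floor: "If such imputed date for subsequent anticancer therapy is before date of last dose (latest of any study drug), then date of last dose" plus one day is used. Progression is not mentioned.

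Four later definitions depend on this start date:

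- **PFS (SAP 7.6.3, Table 1).** PD or death is an event only at or before the earliest of data cutoff, "alternative cancer therapy start date, and discontinuation from study". The row beginning "No INV-PD or death before start of" subsequent therapy censors at the last adequate investigator assessment before that therapy.
- **DOR (SAP 7.6.2).** Responders without an event "will be censored using the same rule for PFS as described in" Table 1.
- **Treatment-emergent (TE) period (SAP 6.1.5).** It closes 30 days after last dose or at the "first date of subsequent anticancer therapy, whichever is earlier".
- **Best overall response (SAP 7.6.1).** It is the "best disease outcome over all response assessments on or before the initiation of subsequent anticancer therapy".

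None of these gives its own rule for a partial date, and SAP section 8 adds none. Protocol 5.4 leaves the details of PFS and DOR censoring to the SAP.

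**The concern.** A mid-month or mid-year date is a reasonable placeholder in a table of therapies. As a censoring boundary it can reverse the order of two events that were recorded in the right order. If PD is on a scan dated the 20th and the next therapy is recorded only by month, the therapy is placed on the 15th. The documented PD then no longer counts, and follow-up is cut back to the previous scan. Under Protocol 4.1.22 scheduled scans in Parts 2 and 3 are 12 weeks apart up to Cycle 13 and 24 weeks apart afterwards.

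The setting is plausible. Subjects may stop for an adverse event (AE) or on the investigator's decision (Protocol 3.8) and are then followed for progression (Protocol 4.4). Therapy starts after PD are collected about every 12 weeks by visit or telephone (Protocol Appendices 5 and 6). At stake are PFS and DOR, both secondary endpoints, in up to 40 subjects in Part 2 Cohort 1 and 26 to 32 in Part 3, and the allocation of AEs in the 30 days after last dose.

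**Working it through.** The plan states no figure on this point, so the rules were applied as written.

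**Notation.** L = last dose, P = PD date, S = true therapy start, I = imputed start.

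**Rules.**
- I = 15th of the recorded month (day missing) or 30 June of the recorded year (year only). If I < L, then I = L + 1 (SAP 6.2.1).
- PD is an event if P ≤ I; otherwise the subject is censored (Table 1, 7.6.2).
- TE end = min(L + 30, I) (6.1.5).

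**Worked cases (2021 calendar).**

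| L | P | S | Recorded | I | PFS/DOR result | TE end, true → SAP |
|---|---|---|---|---|---|---|
| 10 Feb | 20 Mar | 28 Mar | March | 15 Mar | event → censored | 12 Mar → 12 Mar |
| 18 Mar | 24 Mar | 30 Mar | March | 19 Mar (floor) | event → censored | 30 Mar → 19 Mar (11 days short) |
| 1 Oct | 20 Oct | 5 Nov | year | 2 Oct (floor) | event → censored | 31 Oct → 2 Oct (29 days short) |
| 20 Mar | 20 Mar | 28 Mar | March | 21 Mar (floor) | event kept | 28 Mar → 21 Mar (7 days short) |
| 20 Feb | 12 Mar | 5 Mar | March | 15 Mar | censored → event | 5 Mar → 15 Mar (10 days long) |

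**When an event is lost.** If P ≤ L, then I ≥ L ≥ P and the event is always kept. If P is 3 or more days after L and S follows P, the floor never helps. The event is lost exactly when P and S share the recorded month and P is after the 15th (day missing), or share the recorded year and P is after 30 June (year only).

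**How often, given a partial date.** Assume L is equally likely on each of 365 days, with P 3, 7 or 14 days after L. The three gaps give the same counts.

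- Day missing, S = P + 7: P must fall on the 16th to 24th of a 31-day month (9 days), 16th to 23rd of a 30-day month (8) or 16th to 21st of February (6). That is 7×9 + 4×8 + 6 = 101; 101/365 = 27.7%.
- Day missing, S = P + 14: 7×2 + 4×1 + 0 = 18; 18/365 = 4.9%. At 21 and 28 days: 0%.
- Year only, S = P + 7: P from 1 July to 24 December = 177 days; 177/365 = 48.5%. At 14, 21 and 28 days: 170, 163 and 156 days, or 46.6%, 44.7% and 42.7%.
- P only 1 day after L, S = P + 7: 12/365 = 3.3% (day missing) and 1/365 = 0.3% (year only).

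**The reverse error.** Let therapy truly start 7 days before PD, both after last dose. A correct censoring becomes an event when P falls on the 8th to 15th of the recorded month: 12×8 = 96; 96/365 = 26.3%. For year-only dates P must fall from 8 January to 30 June: 174/365 = 47.7%.

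**TE window, S 2 to 29 days after L.**
- Day missing: lengthened when S is on the 1st to 14th, 12×14 = 168, 168/365 = 46.0%; unchanged on the 15th, 12/365; shortened otherwise, 185/365 = 50.7%.
- Year only: lengthened when S is before 30 June, 180/365 = 49.3%; shortened when after, 184/365 = 50.4%.
- Largest shortening: 31 − 15 = 16 days (day missing). For year only it is 29 days through the floor, or 30 if 30 June is itself the last-dose date.

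**Size of one lost event.** With n subjects still at risk, one event is a Kaplan-Meier step of 1/n: 10% at n = 10, 5% at n = 20, 3.3% at n = 30. These values of n are assumptions.

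**The case against.** **Imputation may be meant only for listings.** SAP 6.1.4 links imputed therapy dates to inclusion in the therapy summaries, and neither Table 1 nor 6.1.5 cites 6.2. The intent is therefore uncertain. But 6.2.1 carries no such limit, and no other rule exists. On the narrow reading the censoring date is undefined, so wording is needed either way.

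**Most progressions are safe.** Protocol 4.2 allows treatment until progression is confirmed. Where last dose is on or after PD, the floor protects the event. This stands and limits the problem to PD documented off treatment. It does not protect the TE window, as the fourth worked case shows.

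**The bias has no fixed direction.** A reader might infer that every error favours the drug, since progression usually prompts the next therapy. The documents do not support that. Protocol 4.4 follows subjects who stopped for other reasons until progression whether or not they start a new therapy, so therapy before PD is expected in the very group at risk. The rule then creates events. It also lengthens the TE window about as often as it shortens it, which brings AEs after next-line therapy into the count.

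**Year-only dates should be rare.** Contact about every 12 weeks brackets most start dates. This is a fair point against giving weight to the 43% to 49% figures.

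**Conclusion.** The gap is real. Applied literally, the rule can discard a documented PD that truly preceded new therapy, and can shorten the TE window. Event loss needs both a partial therapy date and PD after last dose. The percentages are conditional on those circumstances and on evenly spread calendar dates and the stated gaps; they are not expected rates of lost events. The documents give no count of partial dates, so the total effect on PFS, DOR or AE tables is unknown and may be nil.

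Two stronger readings should be resisted. One is that the results are biased toward the drug; the errors run both ways. The other is that the Part 2 primary endpoint is compromised. ORR uses the same boundary date, but it would change only if a subject's first CR or PR fell between the imputed and the true start, and nothing in the documents shows that this occurs.

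PFS and DOR are descriptive secondary endpoints with no power basis, so this is a cheap improvement. It is worth making because the cohorts are small and one event is a visible step.

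**What to change.** 1. **SAP 6.2.1.** When only the day is missing and investigator-assessed PD is documented in the same recorded month, take the imputed start for PFS and DOR as the latest of the 15th, last dose + 1 and PD date + 1. All day-missing losses above arise in that month, so they fall to zero. Do not extend this floor to year-only dates: it would count therapy begun months before PD as following it.
2. **Sensitivity analysis.** For year-only dates, and as a check on day-missing dates, report PFS and DOR with the earliest and the latest start consistent with the record.
3. **SAP 6.1.5.** State that the primary AE tables do not shorten the 30-day window on an imputed date unless the recorded month or year proves an earlier start. For example, with last dose on 20 March and therapy recorded as March, therapy began by 31 March, before the 30-day limit of 19 April. Flag AEs that fall after the imputed start.

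The cost is a few sentences and minor programming, with no new data. The downside is that some therapy truly begun before PD in the same month will be counted as after it, and some AEs after next-line therapy may be counted as treatment-emergent. Both are conservative for the drug, and the sensitivity analysis and the flag make them visible.
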